3.5 Criteria for Removal from Protocol Therapy and Off Study Criteria

Prior to documenting removal from study, effort must be made to have all subjects complete a safety visit approximately 3-4 weeks following the last dose of study therapy.

3.5.1 Criteria for removal from protocol therapy

- Completion of protocol therapy
- Clinical progression of disease based on increased symptoms or immune related response criteria (irRC) to also be implemented for disease progression as described in 6.3.2.
- Grade 3 or greater toxicity attributed to treatment that does not resolve to grade 1 within 21 days from time of scheduled treatment.
- Grade 3 or greater autoimmune disease that threatens vital organs.
- Intercurrent illness or medical circumstances. If at any time the constraints of this protocol are detrimental to the patient's health, the patient may be removed from protocol therapy and reasons for withdrawal will be documented.
- Subject decides to withdraw from the study (In this event, the reasons for withdrawal will be documented)
- Investigator discretion
- Positive pregnancy test

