3.3 Drug Administration

Trial treatment should be administered on Day 1 of each cycle after all procedures/assessments have been completed as detailed on the Study Calendar (Section 3.4). Trial treatment may be administered up to 7 days before or after the scheduled Day 1 of each cycle due to administrative reasons.

All trial treatments will be administered on an outpatient basis.

Pembrolizumab 200 mg will be administered as a 30 minute IV infusion every 3 weeks. Every effort should be made to target infusion timing to be as close to 30 minutes as possible.

However, a window of -5 minutes and +10 minutes is permitted (i.e., infusion time is 30 minutes: -5 min/+10 min). Premedication for patients who experience an infusion reaction should be administered 60 minutes (+/- 30 minutes) prior to the infusion.

The Pharmacy Manual contains specific instructions for the preparation of the pembrolizumab infusion fluid and administration of infusion solution. Pembrolizumab is administered through a 0.2 to 5 micron sterile, nonpyrogenic, low-protein binding inline or add-on filter. Do not infuse other medications through the same infusion line.

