3.3.1 Dose Modifications

Adverse events (both non-serious and serious) associated with pembrolizumab exposure may represent an immunologic etiology. These adverse events may occur shortly after the first dose or several months after the last dose of treatment. Pembrolizumab must be withheld for drug-related toxicities and severe or life-threatening AEs as per **Table 4** below. See Section 4 for supportive care guidelines, including use of corticosteroids.

Table 4. Dose Modification Guidelines for Drug-Related Adverse Events

Toxicity	Hold Treatment For Grade	Timing for Restarting Treatment	Treatment Discontinuation
Diarrhea/Colitis	2-3	Toxicity resolves to Grade 0-1	Toxicity does not resolve within 12 weeks of last dose or inability to reduce corticosteroid to 10 mg or less of prednisone or equivalent per day within 12 weeks
	4	Permanently discontinue	Permanently discontinue
AST, ALT, or Increased Bilirubin	2	Toxicity resolves to Grade 0-1	Toxicity does not resolve within 12 weeks of last dose
	3-4	Permanently discontinue (see exception below) ^a	Permanently discontinue
Type 1 diabetes mellitus (if new onset) or Hyperglycemia	T1DM or 3-4	Hold pembrolizumab for new onset Type 1 diabetes mellitus or Grade 3-4 hyperglycemia associated with evidence of beta cell failure	Resume pembrolizumab when patients are clinically and metabolically stable
Hypophysitis	2-4	Toxicity resolves to Grade 0-1. Therapy with pembrolizumab can be continued while endocrine replacement therapy is instituted	Toxicity does not resolve within 12 weeks of last dose or inability to reduce corticosteroid to 10 mg or less of prednisone or equivalent per day within 12 weeks

Toxicity	Hold Treatment For Grade	Timing for Restarting Treatment	Treatment Discontinuation
Hyperthyroidism	3	Toxicity resolves to Grade 0-1	Toxicity does not resolve within 12 weeks of last dose or inability to reduce corticosteroid to 10 mg or less of prednisone or equivalent per day within 12 weeks
	4	Permanently discontinue	Permanently discontinue
Hypothyroidism		Therapy with pembrolizumab can be continued while thyroid replacement therapy is instituted	Therapy with pembrolizumab can be continued while thyroid replacement therapy is instituted
Infusion Reaction	2 ^b	Toxicity resolves to Grade 0-1	Permanently discontinue if toxicity develops despite adequate premedication
	3-4	Permanently discontinue	Permanently discontinue

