Pneumonitis	2	Toxicity resolves to Grade 0-1	Toxicity does not resolve within 12 weeks of last dose or inability to reduce corticosteroid to 10 mg or less of prednisone or equivalent per day within 12 weeks
	3-4	Permanently discontinue	Permanently discontinue
Renal Failure or Nephritis	2	Toxicity resolves to Grade 0-1	Toxicity does not resolve within 12 weeks of last dose or inability to reduce corticosteroid to 10 mg or less of prednisone or equivalent per day within 12 weeks
	3-4	Permanently discontinue	Permanently discontinue
All Other Drug-Related Toxicity ^c	3 or Severe	Toxicity resolves to Grade 0-1	Toxicity does not resolve within 12 weeks of last dose or inability to reduce corticosteroid to 10 mg or less of prednisone or equivalent per day within 12 weeks
	4	Permanently discontinue	Permanently discontinue

Note: Permanently discontinue for any severe or Grade 3 drug-related AE that recurs or any life-threatening event.

^a For patients with liver metastasis who begin treatment with Grade 2 AST or ALT, if AST or ALT increases by greater than or equal to 50% relative to baseline and lasts for at least 1 week then patients should be discontinued.

^b If symptoms resolve within one hour of stopping drug infusion, the infusion may be restarted at 50% of the original infusion rate (e.g., from 100 mL/hr to 50 mL/hr). Otherwise dosing will be held until symptoms resolve and the subject should be premedicated for the next scheduled dose; Refer to **Table 5** – Infusion Reaction Treatment Guidelines for further management details.

^c Patients with intolerable or persistent Grade 2 drug-related AE may hold study medication at physician discretion. Permanently discontinue study drug for persistent Grade 2 adverse reactions for which treatment with study drug has been held, that do not recover to Grade 0-1 within 12 weeks of the last dose.

Dosing interruptions are permitted in the case of medical / surgical events or logistical reasons not related to study therapy (e.g., elective surgery, unrelated medical events, patient vacation, and/or holidays). Subjects should be placed back on study therapy within 6 weeks of the

Abbreviated Title: Pembrolizumab in MTC

Version Date: 3/26/18

scheduled interruption. The reason for interruption should be documented in the patient's study record.

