3.3.2 Dosing Delay

Dosing delay is permitted by 7 days before or after scheduled treatment for logistical purposes (given travel requirements of our patients). If there are changes in the schedule, the subsequent dose may not be given less than 18 days later.

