3.4 Study Calendar

Procedure	Screening/ Baseline ⁵	Treatment Cycles (21 days +/- 7 days) ¹								Cycle 9 and beyond	Post Treatment ⁶	
		C1 D1	C2 D1	C3 D1	C4 D1	C5 D1	C6 D1	C7 D1	C8 D1			
History and PE	X ²	X	X	X	X	X	X	X	X	X	X	X
Vital signs	X ²	X	X	X	X	X	X	X	X	X	X	X
Performance Score	X ²											
Height/Weight	X ³											
HIV, Hep B, C	X											
Pregnancy Test (Urine or Serum beta-HCG)	X ²											
UA ⁴	X ²											
PT/INR and PTT	X ²											
Chemistries ⁷	X ²	X	X	X	X	X	X	X	X	X	X	X
CBC	X ²	X	X	X	X	X	X	X	X	X	X	X
TSH	X ²			X	X	X	X	X	X	X	X	X
T/B/NK subsets	X ²	X	X	X	X	X	X	X	X	X	X	X
Tumor Markers: Calcitonin and CEA	X ²	X	X	X	X	X	X	X	X	X	X	X
Correlative Research Studies (research bloods see Appendix B)	X	continue at 3 month intervals									X ⁸	
Radiological Assessments (MRI or CT Neck, Ch/Abd/Pelvis, Bone Scan) ³	X	continue at 3 month intervals										
EKG ³	X	continue at 3 month intervals									X	
Biopsy (optional) ⁸												
Adverse Events		X										
Concomitant Medications		X										

¹ If patient is delayed, subsequent infusion must be at least 18 days later

Abbreviated Title: Pembrolizumab in MTC

Version Date: 3/26/18

² Must be done within 10 days prior to initiation of study therapy

³ Must be done within 8 weeks prior to initiation of study therapy, and then will be done every 3 months while patients remain on study

⁴ May be omitted if patient is incontinent and cannot provide a urine sample

⁵ Baseline/Screening requirements may also be used for Day 1 requirements if logistically necessary

⁶ Post-Therapy Assessment done 3 weeks after last treatment when logistically feasible (with a possible extension to 4 weeks if logistically necessary). Patients will be offered enrollment in the 04-C-0274 "Follow-Up Study of Subjects Previously Enrolled in Immunotherapy Studies Utilizing Gene Transfer or other Immunotherapeutic Agents" once off study.

⁷ Chemistries: sodium, potassium, chloride, CO₂, creatinine, glucose, BUN, albumin, calcium, magnesium, phosphorus, alkaline phosphatase, ALT, AST, total bilirubin, direct bilirubin, LD, total protein, total CK, uric acid

⁸ When logistically feasible, pre-treatment and post-treatment samples may be obtained from consenting patients.

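### Section 3.5.1 removes patients for a related Grade 3 event unresolved after 21 days from an undefined start, Table 4 allows hold and restart up to 12 weeks from the last dose, and neither is said to govern

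*Combined protocol and SAP*

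**What the plan says.** **Section 3.5.1 (removal from protocol therapy)** lists "Grade 3 or greater toxicity attributed to treatment that does not resolve to grade 1 within 21 days from time of scheduled treatment". It does not say whether the scheduled treatment is the dose already given or the next one due. A separate criterion in the same list is "Grade 3 or greater autoimmune disease that threatens vital organs".

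**Section 3.3.1, Table 4** allows restart once the toxicity is back to Grade 0-1. Its discontinuation column reads "Toxicity does not resolve within 12 weeks of last dose or inability to reduce corticosteroid to 10 mg or less of prednisone" (or equivalent). At Grade 3 this limit applies to diarrhea/colitis, hypophysitis, hyperthyroidism and the catch-all row for other Grade 3 or severe related toxicity. The row for new-onset type 1 diabetes, or Grade 3-4 hyperglycemia with signs of beta cell failure, gives no time limit: "Resume pembrolizumab when patients are clinically and metabolically stable". The Note under the table stops treatment permanently for a recurrent severe or Grade 3 related event and for any life-threatening event.

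**Section 11.1.2** calls for permanent discontinuation when Grade 2 pneumonitis recurs. Table 4's Grade 2 pneumonitis row allows restart and makes no exception for recurrence.

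**Scheduling.** Dosing is every 3 weeks. Section 3.3 adds: "Trial treatment may be administered up to 7 days before or after the scheduled Day 1 of each cycle due to administrative reasons". Section 3.3.2 adds: "If there are changes in the schedule, the subsequent dose may not be given less than 18 days later".

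**The concern.** Sections 3.5.1 and 3.3.1 both decide whether a patient with a related Grade 3 event may receive pembrolizumab again, and they give different limits. Two investigators following the protocol could therefore treat the same event differently. A restart that Table 4 permits could also be a departure from section 3.5.1, and section 7.2.1 requires all deviations to be reported within 7 days.

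The undefined start in section 3.5.1 is a problem in its own right. It gives two answers for the same patient even if Table 4 is set aside.

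The population makes this more than an editorial matter. Section 10.5 describes minimally symptomatic patients who would generally be monitored at this stage, so the rule for stopping after toxicity should be unambiguous.

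**Working it through.** The plan states no figure for the gap between the limits, so there is none to reproduce. The inputs are the 21 days in section 3.5.1, the 12 weeks in Table 4, and the 3-week dosing interval in section 3.3. The last dose given is day 0.

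Table 4 limit: 12 × 7 = day 84.

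| Start of the 3.5.1 clock | 3.5.1 limit | Gap to day 84 |
|---|---|---|
| Dose already given (day 0) | 0 + 21 = day 21 | 84 − 21 = 63 days (9 weeks) |
| Next dose due (nominally day 21) | 21 + 21 = day 42 | 84 − 42 = 42 days (6 weeks) |

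Two examples on the ordinary schedule:

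- **Day 60.** A first Grade 3 colitis resolves to Grade 1 on day 60, with steroids reduced as Table 4 requires. Since 60 < 84, Table 4 permits restart. Since 60 > 42 > 21, the patient already meets the 3.5.1 removal criterion whichever dose starts the clock.
- **Day 30.** A Grade 3 event is still unresolved on day 30. Since 30 > 21, the first start means removal. Since 30 < 42, the second means continued hold.

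**Events outside the conflict.** These are events in rows that already stop permanently at the grade concerned (Grade 3-4 pneumonitis, nephritis and infusion reaction; Grade 3-4 hepatic events apart from the footnoted exception; Grade 4 in several rows), life-threatening events, and events meeting the vital-organ criterion in section 3.5.1.

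**Grade 4 wording.** The hypophysitis and hyperglycemia rows list Grade 4 among the grades that are held and may restart, while the Note stops any life-threatening event. This is a wording mismatch inside Table 4.

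**Pneumonitis.** Section 11.1.2 stops treatment for a second Grade 2 episode. Table 4's Grade 2 row restarts at Grade 0-1, and its Note reaches recurrence only for severe or Grade 3 events. The two differ for that event.

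**Likely numbers.** Section 11.1.2 gives Grade 3 rates of 1.1% (colitis), 0.3% (hypophysitis) and 0.1% (hyperthyroidism). If those rates applied here and the events did not overlap, 32 × (0.011 + 0.003 + 0.001) = 0.48 patients would be expected at the accrual ceiling of 32. That is before asking how many stay unresolved past day 21 or 42, which the documents do not say. It leaves out diarrhea without colitis, hyperglycemia and the catch-all row.

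**Decision rule.** With 15 patients, the probability of 4 or more successes is 5.56% at a true rate of 10% and 90.95% at 40%, matching section 8's 5.6% and 90.9%. The toxicity rule does not enter this calculation.

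**The case against.** The best defence is that the two sections can be obeyed together. Table 4 is headed as guidelines and says when treatment may restart, not that it must. Section 3.5.1 is the list of removal criteria, so following the stricter rule breaches neither. This would work in practice, but the protocol does not say it. On the ordinary schedule it would also leave Table 4's 12-week non-resolution limit with no role for Grade 3 events, including the whole of that limit in the hyperthyroidism row, which holds for Grade 3 only. Table 4's Grade 2 limits and its steroid-reduction limit would keep their effect.

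Nor can Table 4 simply be taken to govern. Section 3.3.1 makes withholding per Table 4 mandatory and section 4.1.3 refers to 3.3.1 for dose modification, but neither mentions section 3.5.1. Investigator discretion appears in 3.5.1 as a ground for removal, not for continuing past another criterion.

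Two stronger readings are tempting and are not supported:

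- **That the limits conflict by a fixed margin however the clock is read.** A reader might apply the 7-day window once and conclude that 3.5.1 always expires by 21 + 7 + 21 = day 49. If the last dose was 7 days early and the next is due 7 days late, the result is 21 + 7 + 7 + 21 = day 56. Section 3.3.1 also allows unrelated interruptions with return within 6 weeks. If one began at the day-21 dose and the rescheduled dose counted as the scheduled treatment, the limit would be 21 + 42 + 21 = day 84, equal to Table 4's. The 18-day rule limits when a dose may be given and does not fix the scheduled date. Only the nominal figures should be relied on.
- **That all Grade 4 hypophysitis and hyperglycemia falls in the gap.** The Note already stops life-threatening events permanently.

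The pneumonitis mismatch is fairly called secondary. Section 11.1.2 is pharmaceutical information and involves no 21-day clock. It is still a contradiction, and no text says that Table 4 overrides it.

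**Conclusion.** The protocol contradicts itself on a safety rule and is wrong as written. On the ordinary 3-week schedule, from day 21 or day 42 to day 84 after the last dose, section 3.5.1 requires removal for an unresolved related Grade 3 event, while Table 4 permits hold and restart. The nominal gap is 63 or 42 days, depending on an undefined starting point. For Grade 3 hyperglycemia with beta cell failure, Table 4 sets no end.

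The conclusion assumes no unrelated interruption has moved the schedule. It covers only the Grade 3 rows named above and excludes life-threatening events, permanent-stop rows and vital-organ autoimmune events. The number of patients affected is likely small but cannot be estimated properly. The sample size and the 4-of-15 rule are unaffected. It should be fixed because it concerns patient safety and consistent conduct, not because it threatens the primary analysis.

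**What to change.** Reconcile section 3.5.1, Table 4 with its Note, and section 11.1.2:

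- Define the event that starts each clock, including what happens when a dose has been rescheduled.
- State which section takes precedence, by toxicity if the limits are meant to differ, and cross-refer between them.
- Align the Grade 4 entries in the hypophysitis and hyperglycemia rows with the Note.
- State in the same place how recurrent Grade 2 pneumonitis is handled.

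Which limit or rule applies is for the clinical team, and none is proposed here. The cost is a wording amendment, with no added visits, procedures or patients.

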3.5.2 Off-Study Criteria

Patients will be removed from the study for the following:

- Subjects proceeds to alternative treatments
- Death
- Patient requests to be taken off study. Reasons for withdrawal will be documented.
- Noncompliance with protocol guidelines (patient removed at discretion of Principal Investigator).
- Investigator decides to end the study
- Screen failure

Patients will be offered enrollment in the 04-C-0274 "Follow-Up Study of Subjects Previously Enrolled in Immunotherapy Studies Utilizing Gene Transfer or other Immunotherapeutic Agents" once off study.

3.5.3 Off Protocol Therapy and Off-Study Procedure

Authorized staff must notify Central Registration Office (CRO) when a subject is taken off protocol therapy and when a subject is taken off-study. A Participant Status Updates Form from

the web site (<http://home.ccr.cancer.gov/intra/eligibility/welcome.htm>) main page must be completed and sent via encrypted email to: NCI Central Registration Office [contact].

4 CONCOMITANT MEDICATIONS/MEASURES

Medications or vaccinations specifically prohibited in the exclusion criteria are not allowed during the ongoing trial. If there is a clinical indication for one of these or other medications or vaccinations specifically prohibited during the trial, discontinuation from trial therapy or vaccination may be required. The investigator may discuss any questions regarding this with the Merck Clinical team. The final decision on any supportive therapy or vaccination rests with the investigator and/or the subject's primary physician.

4.1.1 Acceptable Concomitant Medications

All treatments that the investigator considers necessary for a subject's welfare may be administered at the discretion of the investigator in keeping with the community standards of medical care. All concomitant medication will be recorded on the case report form (CRF) including all prescription, over-the-counter (OTC), herbal supplements, and IV medications and fluids. If changes occur during the trial period, documentation of drug dosage, frequency, route, and date may also be included on the CRF.

All concomitant medications received within 28 days before the first dose of trial treatment and 30 days after the last dose of trial treatment should be recorded. Concomitant medications administered after 30 days after the last dose of trial treatment should be recorded for SAEs as defined in Section **7.1.5**.

4.1.2 Prohibited Concomitant Medications

Subjects are prohibited from receiving the following therapies during the Screening and Treatment Phase (including retreatment for post-complete response relapse) of this trial:

- Antineoplastic systemic chemotherapy or biological therapy
- Immunotherapy not specified in this protocol
- Chemotherapy not specified in this protocol
- Investigational agents other than pembrolizumab
- Radiation therapy
 - Note: Radiation therapy to a symptomatic solitary lesion or to the brain may be allowed at the investigator's discretion.
- Live vaccines within 30 days prior to the first dose of trial treatment and while participating in the trial. Examples of live vaccines include, but are not limited to, the following: measles, mumps, rubella, varicella/zoster, yellow fever, rabies, BCG, and typhoid vaccine.

- Systemic glucocorticoids for any purpose other than to modulate symptoms from an event of clinical interest of suspected immunologic etiology. The use of physiologic doses of corticosteroids may be approved after consultation with the Sponsor.

The Exclusion Criteria describes other medications which are prohibited in this trial.

There are no prohibited therapies during the Post-Treatment Follow-up Phase.

4.1.3 Supportive Care Guidelines

Subjects should receive appropriate supportive care measures as deemed necessary by the treating investigator. Suggested supportive care measures for the management of adverse events with potential immunologic etiology are outlined below. Where appropriate, these guidelines include the use of oral or intravenous treatment with corticosteroids as well as additional anti-inflammatory agents if symptoms do not improve with administration of corticosteroids. Note that several courses of steroid tapering may be necessary as symptoms may worsen when the steroid dose is decreased. For each disorder, attempts should be made to rule out other causes such as metastatic disease or bacterial or viral infection, which might require additional supportive care. The treatment guidelines are intended to be applied when the investigator determines the events to be related to pembrolizumab.

Note: if after the evaluation the event is determined not to be related, the investigator does not need to follow the treatment guidance (as outlined below). Refer to Section **3.3.1** for dose modification.

It may be necessary to perform conditional procedures such as bronchoscopy, endoscopy, or skin photography as part of evaluation of the event.

- **Pneumonitis:**
 - For **Grade 2 events**, treat with systemic corticosteroids. When symptoms improve to Grade 1 or less, steroid taper should be started and continued over no less than 4 weeks.
 - For **Grade 3-4 events**, immediately treat with intravenous steroids. Administer additional anti-inflammatory measures, as needed.
 - Add prophylactic antibiotics for opportunistic infections in the case of prolonged steroid administration.

- **Diarrhea/Colitis:**

Subjects should be carefully monitored for signs and symptoms of enterocolitis (such as diarrhea, abdominal pain, blood or mucus in stool, with or without fever) and of bowel perforation (such as peritoneal signs and ileus).

- All subjects who experience diarrhea/colitis should be advised to drink liberal quantities of clear fluids. If sufficient oral fluid intake is not feasible, fluid and electrolytes should be substituted via IV infusion. For Grade 2 or higher diarrhea, consider GI consultation and endoscopy to confirm or rule out colitis.
- For **Grade 2 diarrhea/colitis**, administer oral corticosteroids

- For **Grade 3 or 4 diarrhea/colitis**, treat with intravenous steroids followed by high dose oral steroids.
- When symptoms improve to Grade 1 or less, steroid taper should be started and continued over no less than 4 weeks.
- **Type 1 diabetes mellitus (if new onset, including diabetic ketoacidosis [DKA]) or ≥ Grade 3 Hyperglycemia, if associated with ketosis (ketonuria) or metabolic acidosis (DKA)**
 - For **T1DM or Grade 3-4 Hyperglycemia**
 - Insulin replacement therapy is recommended for Type I diabetes mellitus and for Grade 3-4 hyperglycemia associated with metabolic acidosis or ketonuria.
 - Evaluate patients with serum glucose and a metabolic panel, urine ketones, glycosylated hemoglobin, and C-peptide.
- **Hypophysitis:**
 - For **Grade 2** events, treat with corticosteroids. When symptoms improve to Grade 1 or less, steroid taper should be started and continued over no less than 4 weeks. Replacement of appropriate hormones may be required as the steroid dose is tapered.
 - For **Grade 3-4** events, treat with an initial dose of IV corticosteroid followed by oral corticosteroids. When symptoms improve to Grade 1 or less, steroid taper should be started and continued over no less than 4 weeks. Replacement of appropriate hormones may be required as the steroid dose is tapered.
- **Hyperthyroidism or Hypothyroidism:**

Thyroid disorders can occur at any time during treatment. Monitor patients for changes in thyroid function (at the start of treatment, periodically during treatment, and as indicated based on clinical evaluation) and for clinical signs and symptoms of thyroid disorders.

 - **Grade 2** hyperthyroidism events (and **Grade 2-4** hypothyroidism):
 - In hyperthyroidism, non-selective beta-blockers (e.g. propranolol) are suggested as initial therapy.
 - In hypothyroidism, thyroid hormone replacement therapy, with levothyroxine or liothyronine, is indicated per standard of care.
 - **Grade 3-4** hyperthyroidism
 - Treat with an initial dose of IV corticosteroid followed by oral corticosteroids. When symptoms improve to Grade 1 or less, steroid taper should be started and continued over no less than 4 weeks. Replacement of appropriate hormones may be required as the steroid dose is tapered.
- **Hepatic:**

- For **Grade 2** events, monitor liver function tests more frequently until returned to baseline values (consider weekly).
 - Treat with IV or oral corticosteroids
 - For **Grade 3-4** events, treat with intravenous corticosteroids for 24 to 48 hours.
 - When symptoms improve to Grade 1 or less, a steroid taper should be started and continued over no less than 4 weeks.
- **Renal Failure or Nephritis:**
 - For **Grade 2** events, treat with corticosteroids.
 - For **Grade 3-4** events, treat with systemic corticosteroids.
 - When symptoms improve to Grade 1 or less, steroid taper should be started and continued over no less than 4 weeks.
 - **Management of Infusion Reactions:**

Signs and symptoms usually develop during or shortly after drug infusion and generally resolve completely within 24 hours of completion of infusion.

Table 5 below shows treatment guidelines for subjects who experience an infusion reaction associated with administration of pembrolizumab (MK-3475).

Table 5. Infusion Reaction Treatment Guidelines

NCI CTCAE Grade	Treatment	Premedication at subsequent dosing

Grade 1 Mild reaction; infusion interruption not indicated; intervention not indicated
	
Increase monitoring of vital signs as medically indicated until the subject is deemed medically stable in the opinion of the investigator.
	
None

Grade 2 Requires infusion interruption but responds promptly to symptomatic treatment (e.g., antihistamines, NSAIDS, narcotics, IV fluids); prophylactic medications indicated for <=24 hrs
	
Stop Infusion and monitor symptoms. Additional appropriate medical therapy may include but is not limited to: IV fluids Antihistamines NSAIDS Acetaminophen Narcotics
 
Increase monitoring of vital signs as medically indicated until the subject is deemed medically stable in the opinion of the investigator.
 
If symptoms resolve within one hour of stopping drug infusion, the infusion may be restarted at 50% of the original
	
Subject may be premedicated 1.5h (± 30 minutes) prior to infusion of pembrolizumab (MK-3475) with:
 
Diphenhydramine 50 mg po (or equivalent dose of antihistamine).
 
Acetaminophen 500-1000 mg po (or equivalent dose of antipyretic).

NCI CTCAE Grade	Treatment	Premedication at subsequent dosing
	
infusion rate (e.g., from 100 mL/hr to 50 mL/hr). Otherwise dosing will be held until symptoms resolve and the subject should be premedicated for the next scheduled dose.
 
Subjects who develop Grade 2 toxicity despite adequate premedication should be permanently discontinued from further trial treatment administration.
	

Grades 3 or 4
 
Grade 3: Prolonged (i.e., not rapidly responsive to symptomatic medication and/or brief interruption of infusion); recurrence of symptoms following initial improvement; hospitalization indicated for other clinical sequelae (e.g., renal impairment, pulmonary infiltrates)
 
Grade 4: Life-threatening; pressor or ventilatory support indicated
	
Stop Infusion.
 
Additional appropriate medical therapy may include but is not limited to:
 
 IV fluids Antihistamines NSAIDS Acetaminophen Narcotics Oxygen Pressors Corticosteroids Epinephrine 
Increase monitoring of vital signs as medically indicated until the subject is deemed medically stable in the opinion of the investigator.
 
Hospitalization may be indicated.
 
Subject is permanently discontinued from further trial treatment administration.
	
No subsequent dosing

Appropriate resuscitation equipment should be available in the room and a physician readily available during the period of drug administration.
		

